3.5.2. Vital Signs

Vital signs include temperature, systolic and diastolic blood pressure, and heart rate. Details on the collection of vital signs can be found in section 8.2.2 of the protocol.

3.5.3. Laboratory Data

Details of the laboratory tests can be found in Appendix 2 of the protocol.

4. ANALYSIS SETS (POPULATIONS FOR ANALYSIS)

Data for all participants will be assessed to determine if participants meet the criteria for inclusion in each analysis population prior to unblinding and releasing the database and classifications will be documented per standard operating procedures.

Table 2. Analysis Sets

Population	Description
Full analysis set	The full analysis set includes all enrolled participants. "Enrolled" means a participant's, or their legally authorized representative's, agreement to participate in a clinical study following completion of the informed consent process. Potential participants who are screened for the purpose of determining eligibility for the study, but do not participate in the study, are not considered enrolled, unless otherwise specified by the protocol.
Safety analysis set	The safety analysis set includes all enrolled participants who receive at least one dose of study intervention. Unless otherwise specified the safety analysis set will be the default analysis set used for all analyses.
Per protocol analysis set (Evaluable for MTD)	The per protocol analysis set includes all enrolled participants who had at least one dose of study treatment and either experienced DLT or do not have major treatment deviations during the DLT observation period. To be DLT evaluable, a participant must have received at least 75% of their planned doses in each cycle for the first two cycles (i.e., ≥ 11 doses received in each of the first two cycles) and has received all scheduled safety assessments during the DLT window.
Modified Intent to Treat (mITT)	The modified intent to treat (mITT) is the analysis population that will follow the ITT principle and include participants receiving at least 1 dose of study medication with baseline assessment and at least 1 post baseline assessment, disease progression, or death before the first tumor assessment. The mITT population may be used for interim analysis and conference presentations when the study is still ongoing.
PK analysis sets	The PK parameter analysis population is defined as all enrolled participants treated who do not have protocol deviations influencing PK assessment, and have sufficient information to estimate at least 1 of the PK parameters of interest.

Population	Description
	The PK concentration population is defined as all enrolled participants who are treated and have at least 1 postdose analyte concentration.
Response Evaluable set	The response evaluable population will include all participants who received at least one dose of study treatment and had measurable disease at baseline and at least one post baseline disease assessment.
PD/Biomarker analysis set(s)	The PD/Biomarker analysis population is defined as all enrolled participants with at least 1 of the PD/Biomarkers evaluated at pre and/or post dose.
Immunogenicity analysis set	The immunogenicity analysis set includes all enrolled participants who receive at least one dose of study treatment and have at least one sample tested for ADA.

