4.3.3. Dose Limiting Toxicity Definition

For the purpose of dose escalation, any of the following AEs will be classified as DLTs:

- Occur in the first cycle of treatment, or within 28 days after the start of the study treatment; and
- Are at least possibly related to PF-07209960; A participant is classified as DLT evaluable if he/she experiences a DLT or if he/she otherwise in the absence of a DLT receives 2 doses of the study intervention during Cycle 1 and has received all scheduled safety assessments during the DLT window. If a participant fails to meet these criteria, he/she may be replaced. Monitoring for DLTs will occur during Part 1.

Significant AEs considered to be related to the study intervention or treatment under investigation that occur after the DLT observation period will be reviewed in context of all safety data available. That review may result in re-evaluation of the dosing level or regimen.

Hematologic DLTs:

1. Grade 4 neutropenia (absolute neutrophil count [ANC] <500/mm³) lasting >7 days;
2. Febrile neutropenia (defined as an ANC <1000/mm³, with a single temperature of >38.3°C [101°F], or a sustained temperature of ≥38°C [100.4°F] for more than one hour);
3. Neutropenic infection (defined as an ANC <1000/mm³ with Grade ≥3 infection);
4. Grade 3 thrombocytopenia (platelet count <50,000 mm³) with any bleeding;
5. Grade 4 thrombocytopenia (platelet count <25,000/mm³);
6. Grade 4 anemia (life-threatening consequences; urgent intervention indicated).

Non-Hematologic DLTs:

- Any Grade ≥3 non-hematologic treatment related AE is a DLT with the following exceptions:
 1. Grade 3 nausea, vomiting, diarrhea, or fatigue that can be controlled with or without medical therapy to Grade ≤2 within 72 hours;
 2. Grade ≥3 laboratory abnormalities without a clinical correlate and that do not require medical intervention, or are corrected to Grade ≤2 with supplementation/appropriate management within 72 hours;

Immune-related AE (irAE) that meet the following criteria:

1. Grade 4 irAE regardless of duration (for lab abnormalities without clinical correlate and do not require medical intervention please refer to criteria above);

2. Grade ≥ 3 colitis regardless of duration (diagnosis of colitis must be supported by diagnostic testing);
3. Grade ≥ 3 non-infectious pneumonitis regardless of duration;
4. Grade 2 non-infectious pneumonitis that does not resolve to \leq Grade 1 within 72 hours of the initiation of maximal supportive care;

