6.1.1. Administration

PF-07209960 will be administered once every 2 weeks as a flat dose SC injection or IV infusion over 1 hour (± 10 minutes).

Each participant may receive PF-07209960 until disease progression, unacceptable toxicity, withdrawal of consent, or study termination. Treatment beyond disease progression may be discussed with sponsor if the investigator assesses that it is the participant's best interest to continue with treatment and would not derive as much benefit from alternative therapy and has met the criteria for treatment beyond progression as outlined in [Section 4](#) .

Subcutaneous administration

Qualified and trained investigator site personnel will administer PF-07209960 to participants by SC injection. Ideally, each injection may be up to 2 mLs in volume. However, if the maximum volume allowed per institution's policy is lower, the number of injections may

increase to accommodate this difference in volume to ensure the correct final dose is delivered.

Study drug should be administered to the abdomen (with preference given to the lower quadrants when possible). Refer to [Appendix 12](#), for details on administration of multiple injections to the abdomen. Study staff should refer to the IP Manual for specific instructions on the handling and preparation of study drug.

Cycle duration: A cycle is defined as 28 days, regardless of missed doses or dose delays.

Intravenous administration

Based on the available emerging clinical data (including safety/tolerability, PK, PD) from the dose escalation cohorts with SC Q2W administration, IV infusion Q2W administration may be explored in successive dose cohorts. If IV administration is introduced, PF-07209960 will be administered over 1 hour (± 10 minutes) time period without adjustment for body size at every cycle as indicated in the IP manual.

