2.2. Study Design

This is a Phase 1, open label, multicenter, multiple dose, dose escalation, safety, PK and PD study of PF-07209960 in participants with selected locally advanced or metastatic solid tumors (anti-PD-I/PD-LI resistant NSCLC, SCCHN, RCC, UC; or anti-PD I naive OvCa and MSS CRC for whom no standard therapy is available, or would not be an appropriate option in the opinion of the participant and their treating physician, or participants who have refused standard therapy.

The study contains 2 parts, single agent dose escalation (Part 1) followed by a dose expansion at the RP2D (Part 2). The overall study design is depicted in the schema (Section 1.2 in the protocol). Successive cohorts of participants in Part 1 will receive escalating doses of PF-07209960 as SC or IV administration every 2 weeks. The first and second participant in each dose level must be enrolled >72 hours apart. BLRM guided by EWOC principle will be used to guide dose escalation process and determine the MTD/IRP2D. Part 1 will estimate the MTD/IRP2D in sequential dose escalation cohorts for PF-07209960 as single agent in participants with selected solid tumors. After the MTD/IRP2D for PF-07209960 single agent is determined, Part 2 expansion will be initiated in participants with selected solid tumors as informed by Part 1.

Number of Participants: *The total number of participants enrolled to study intervention is estimated to range from approximately 74 to 172. Approximately 14-22 participants are expected to be enrolled in Part 1 dose escalation. Each cohort in Part 2 will enroll 20-30 participants. Approximately 60-90 participants will be initially enrolled in the first three cohorts, with the option to further enroll approximately 40-60 participants in an additional two cohorts.*

Intervention Groups and Duration: *PF-07209960 will be administered as monotherapy, SC or IV infusion over 1 hour (± 10 minutes) on Days 1 and 15 in 28 day cycles as described in Section 4.3.1 in the protocol. Treatment with study intervention will continue until either disease progression, unacceptable toxicity, participant refusal, or whichever is earliest, unless the investigator and medical monitor agree to treatment beyond disease progression based on individual benefit/risk assessments or agree to discontinue treatment or the study is terminated.*

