3.5.1. Adverse Events

Severity of adverse events will be graded according to Common Terminology Criteria for Adverse Events (CTCAE) version 5.0. Treatment-emergent AE are defined as AEs with onset date during the on-treatment period.

For the purpose of dose escalation, any of the AEs listed in section 4.3.3 of the protocol that occur during the DLT observation period (i.e., first cycle of treatment) for DLT-evaluable participants, that are attributable to the study intervention, will be classified as DLTs.

Definitions of an AE and a SAE can be found in Appendix 3 of the protocol.

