6.1.1. Dose-Limiting Toxicities (DLTs)

- Analysis set: Per protocol analysis set
- Analysis methodology:

For the purpose of dose escalation, the DLT observation period/window will be the first cycle (defined as 28 days after the start of study treatment), for each participant. Whether an adverse event a participant experienced during the DLT window is determined as a DLT or not is based on the DLT definitions provided in Section 4.3.3 of the protocol.

The DLT events will be summarized by dose level. A listing of the DLT events will also be provided in which the participant's primary diagnosis (malignancy), dose level the participant was enrolled to, DLT event start day and stop day relative to the C1D1 dose date, the DLT event term, NCI CTCAE grade, relatedness to the investigational product (PF-07209960), outcome of the event, along with other variables deemed important, will be included.

- Missing data: All enrolled participants in Part 1 should have an indicator variable derived to be either 1 (yes) or 0 (no) based on the DLT definitions (provided in

Section 4.3.3 of the protocol) and participant's safety data during the DLT observation window. If a participant fails to have a value on the indicator variable because the participant being non-DLT-evaluable, the participant may be replaced.

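### The SAP's DLT-evaluable rule requires at least 11 doses per cycle over two cycles, but only 2 are given per cycle, so the MTD analysis set cannot be formed as written

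*SAP*

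**What the plan says.** SAP section 4, Table 2 describes the per protocol (evaluable for MTD) set in two sentences. The first closely follows protocol 9.3: at least one dose, and either a DLT or no major treatment deviation in the DLT observation period. The second adds that a DLT-evaluable participant "must have received at least 75% of their planned doses in each cycle for the first two cycles", glossed as at least "11 doses received in each of the first two cycles", together with all scheduled safety assessments in the DLT window.

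Other places say something different:

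- **Dosing.** SAP 2.2 gives the drug "on Days 1 and 15 in 28 day cycles". Protocol 6.1.1 says "PF-07209960 will be administered once every 2 weeks as a flat dose SC injection", or as an IV infusion at the same interval, and defines a cycle as 28 days.
- **Evaluability.** Protocol 4.3.3 counts a participant who has a DLT as evaluable. Without a DLT, the participant is evaluable if he or she "receives 2 doses of the study intervention during Cycle 1" and has had all scheduled safety assessments in the window.
- **Window.** SAP 6.1.1 states that "the DLT observation period/window will be the first cycle (defined as 28 days after the start of study treatment"). SAP 3.5.1 uses the same window and classifies events as DLTs in it ("i.e., first cycle of treatment) for DLT-evaluable participants").
- **Use.** Protocol 9.4.1 determines the MTD on this per protocol set, and SAP 6.1.1 analyses DLTs on it.

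**The concern.** The required dose count is impossible on the trial's schedule, and the sentence also differs from the protocol in its time span and in its treatment of participants with a DLT. The set it defines is central to Part 1. First-cycle DLTs are a primary endpoint. The Bayesian logistic regression model (BLRM) takes its DLT counts and denominators from evaluable participants, and SAP 5.2 says the resulting DLT-rate estimates guide the dose-level review meetings. Protocol 9.2.1 requires at least 6 evaluable participants at the dose estimated to be the MTD. Participants who are not evaluable may be replaced (protocol 4.3.3, SAP 6.1.1), so the definition also bears on enrolment. If it cannot be applied, someone must choose another rule, possibly after DLT data are known.

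**Working it through.** **1. Doses per cycle.** One dose every 14 days in a 28-day cycle: 28 / 14 = 2.

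**2. The SAP's own figure.** The SAP equates 75% of planned doses with 11.

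- Per cycle: 0.75 × 2 = 1.5, so 2 whole doses. The figure of 11 is not reproduced.
- Both cycles pooled: 0.75 × 4 = 3. Not 11 either.
- Working backwards and rounding up, 11 arises only from 14 planned doses per cycle (0.75 × 14 = 10.5). Rounding down or to the nearest whole number, it arises only from 15 (0.75 × 15 = 11.25). Neither schedule appears in the documents.

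**3. Time span.** The second-cycle condition requires the Cycle 2 Day 15 dose, nominally study Day 28 + 15 = 43. The window closes at 28 days. Correcting 11 to 2 alone would still leave out a participant who completed the window without a DLT but stopped before Day 43.

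**4. Effect on the analysis set**, assuming all 6 treated participants meet the protocol rule:

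| DLTs in 6 treated | Protocol 4.3.3 | SAP sentence, literal | SAP sentence, DLT cases admitted |
|---|---|---|---|
| 0 | 0/6 = 0% | nobody evaluable | nobody evaluable |
| 1 | 1/6 = 16.7% | nobody evaluable | 1/1 = 100% |
| 2 | 2/6 = 33.3% | nobody evaluable | 2/2 = 100% |

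**5. Effect on the model (illustration only).** The prior derivation is left to a technical supplement and the dose levels are blacked out, so these inputs are assumptions:

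- three doses on a half-log ladder, with 0/3, 0/3 and 1/6 DLTs;
- the model of protocol Appendix 8, logit π(d) = log α + β log(d/d*), with log α ~ N(logit 0.25 to logit 0.33, SD 2) and log β ~ N(0, 1), independent;
- reference dose d* varied over the first seven half-log doses.

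The overdose limit is P(DLT rate ≥ 0.33) below 25% (protocol 4.3.2).

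| Data entering the model | P(DLT rate ≥ 0.33), dose 3 | P(DLT rate ≥ 0.33), dose 1 |
|---|---|---|
| 0/3, 0/3, 1/6 | 0.015 to 0.143 | not limiting |
| 1/1 at dose 3 only | 0.56 to 0.97 | 0.28 to 0.62 |

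With the correct denominators, dose 3 is within the limit throughout. With only the DLT case, every dose, including the first, is above the limit. With d* one half-log above dose 3, the values are about 0.05 for the full data, and 0.68 to 0.73 (dose 3) and 0.33 to 0.37 (dose 1) for the DLT case alone.

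**The case against.** The best defence is that the set survives on a sensible reading. The first sentence of the Table 2 entry defines it without a dose count, as does protocol 9.3, and protocol 4.3.3 gives a correct evaluability rule. Protocol section 9 lets the SAP modify the protocol but requires major changes to primary endpoint definitions or analyses to appear in a protocol amendment as well, and the protocol contains no such change. Dose decisions also rest on a review meeting that sees all safety data and may go below the model's recommendation (protocol 9.6). A rule that excluded every participant without a DLT would be noticed at the first cohort.

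Much of this stands as a statement about practice: collapse of the set follows from applying the SAP as written and is not a certain outcome. A silently wrong MTD is less likely than an ad hoc correction during the trial. The definition is still not rescued, because the favourable reading works only by ignoring the second sentence, and neither document says which text governs. SAP 3.5.1 and 6.1.1 both depend on DLT-evaluable status, which that sentence defines. SAP section 2 says italics mark text taken directly from the protocol. In the extracted text the sentence is italicised, yet protocol 9.3 does not contain it, so a programmer could take it as protocol wording.

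It is also fair that the model illustration depends on assumed inputs, the reference dose in particular. The ranges above are wide for that reason, and the point does not rest on them.

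**Conclusion.** The concern holds. The SAP's evaluability sentence asks for at least 11 doses per cycle where 2 are possible, runs over two cycles where the DLT window is one, and drops the protocol's provision for participants with a DLT. Applied as written, it gives 0 evaluable participants, against the minimum of 6 at the MTD, or a set made up only of DLT cases with an observed rate of 100%. The 2-versus-11 finding needs no assumption beyond the documents' own schedule. The model probabilities rest on assumed priors, doses and data; across the reference doses tried, every value with the DLT case alone exceeds 25%. Why 11 was written is not stated; a carry-over from a study with 14 planned doses per cycle would fit the arithmetic but is conjecture. This must be corrected before the DLT data are used.

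**What to change.** In SAP Table 2, replace the second sentence of the per protocol entry with the protocol 4.3.3 definition: a participant is DLT evaluable if he or she has a DLT in the 28-day window or, without one, received both Cycle 1 doses and all scheduled safety assessments in that window. Remove the 75% threshold, the count of 11 and the reference to two cycles together, since changing 11 to 2 alone would leave the two-cycle conflict. Do this before the first dose-level review, so that the rule is fixed before DLT data are seen. The cost is one sentence in a SAP amendment. The protocol, dosing and data collection do not change.

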 - d. Participants who had received prior anti-PD-1 must be ≥ 90 days from their last anti-PD-1 dose. Participants who received prior anti-PD-L1 are not subject to this restriction.
 - e. Participants with OvCa or MSS CRC must not have received prior anti-PD-1/PD-L1 therapy.
 - f. Demonstrated radiographic progression on most recent tumor assessment imaging.
 - g. For Part 2, in addition:
 - a) Participants with NSCLC must have received either ≥ 2 prior lines of therapy including at ≥ 1 prior regimen containing chemotherapy and ≥ 1 prior regimen containing anti-PD-1/PD-L1 or a prior regimen of anti-PD-1/PD-L1 in combination with chemotherapy (eg, atezolizumab with chemotherapy). In addition, NSCLC with a BRAF V600E mutation must have also received BRAF inhibitor with or without MEK inhibitor.
 - b) Participants with RCC must have received either ≥ 2 prior lines of therapy including ≥ 1 prior regimen containing anti-PD-1/PD-L1 and ≥ 1 prior regimen containing a small molecule kinase inhibitor or a prior regimen of anti-PD-1/PD-L1 in combination with a small molecule kinase inhibitor (eg, avelumab with axitinib).
 - c) Participants with UC must have received ≥ 2 prior lines of therapy including platinum-containing chemotherapy and anti-PD-1/PD-L1, or a single regimen of platinum-containing chemotherapy followed by anti-PD-1/PD-L1 maintenance therapy.
 - d) Participants with MSS CRC must have received ≥ 2 prior lines of therapy including treatment regimens containing combinations of pyrimidine analog, oxaliplatin, irinotecan, anti-EGFR (RAS wild type), encorafenib (if BRAF V600E-positive) and anti-HER2 (if HER2 amplified and RAS and BRAF wild type).

- e) Participants with OvCa must have received ≥ 2 prior lines of therapy including at least 1 regimen with platinum-based chemotherapy and progressed on last two consecutive regimens without evidence of clinical benefit.
2. Participants entering the study in the expansion cohort have ≥ 1 measurable lesion per RECIST version 1.1 that has not been previously irradiated.
3. Tumor tissue available or accessible for biopsy:

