of platinum-containing chemotherapy followed by anti-PD-1/PD-L1 maintenance therapy.

- d) Participants with MSS CRC must have received ≥ 2 prior lines of therapy including treatment regimens containing combinations of pyrimidine analog, oxaliplatin, irinotecan, anti-EGFR (RAS wild type), encorafenib (if BRAF V600E-positive) and anti-HER2 (if HER2-amplified and RAS and BRAF wild type).
- e) Participants with OvCa must have received ≥ 2 prior lines of therapy including at least 1 regimen with platinum-based chemotherapy and progressed on last two consecutive regimens without evidence of clinical benefit.

3. Participants entering the study in ≥ 1 measurable lesion (at least 10 mm in the longest diameter by CT scan/MRI for non-lymph nodes and at least 15 mm in the short axis for lymph nodes) as defined by RECIST version 1.1 that has not been previously irradiated.
4. Must have tumor tissue available for submission to the sponsor:
 - a. Participants enrolled in Part 1 and Part 2 should consent to undergo biopsy during screening (pre-treatment) or be able to provide archival FFPE material containing tumor that is of diagnostic quality and representative of their diagnosed malignancy taken ≤ 1 year prior to study start. If the archival sample is older than 1 year and a biopsy during screening cannot be performed, the investigator must contact the sponsor to discuss eligibility prior to enrollment.
 - b. Participants enrolled in Part 2 dose expansion must have a tumor amenable to biopsy and consent to planned mandatory pre- and on-treatment biopsy procedures until the sponsor deems that an adequate number of participants (10-15 paired fresh biopsies per cohort) have been successfully biopsied, at which point participants will only be required to submit pre-treatment biopsies (either archival tissue or de novo biopsy as above). Special considerations will be made for participants with poorly accessible tumors or deemed medically unsafe as determined by the investigator after discussion and agreement by the sponsor.
5. ECOG PS 0-2 for Part 1, 0-1 for Part 2.
6. Adequate hematologic function, including:
 - a. ANC $\geq 1,500/\text{mm}^3$ or $\geq 1.5 \times 10^9/\text{L}$;
 - b. Platelets $\geq 100,000/\text{mm}^3$ or $\geq 100 \times 10^9/\text{L}$;

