9.3. Analysis Sets

1. Full analysis set.

The full analysis set includes all enrolled participants.

"Enrolled" means a participant's, or their legally authorized representative's, agreement to participate in a clinical study following completion of the informed consent process. Potential participants who are screened for the purpose of determining eligibility for the study, but do not participate in the study, are not considered enrolled, unless otherwise specified by the protocol.

2. Safety analysis set.

The safety analysis set includes all enrolled participants who receive at least one dose of study intervention. Unless otherwise specified, the safety analysis set will be the default analysis set used for all analyses.

3. Per protocol analysis set (evaluable for MTD).

The per protocol analysis set includes all enrolled and evaluable participants who had at least one dose of study treatment and either experienced DLT or do not have major treatment deviations during the DLT observation period.

4. mITT Population.

The mITT is the analysis population that will follow the ITT principle and include participants receiving at least 1 dose of study medication with baseline assessment and at least 1 post baseline assessment, disease progression, or death before the first tumor assessment. The mITT population may be used for interim analysis and conference presentations when the study is still ongoing.

5. PK analysis sets.

The PK parameter analysis population is defined as all enrolled participants treated who do not have protocol deviations influencing PK assessment, and have sufficient information to estimate at least 1 of the PK parameters of interest.

The PK concentration population is defined as all enrolled participants who are treated and have at least 1 postdose analyte concentration.

6. Response Evaluable Set.

The response evaluable population will include all participants who received at least one dose of study treatment and had baseline disease assessment and at least one post baseline disease assessment.

7. PD/Biomarker analysis set(s).

The PD/Biomarker analysis population is defined as all enrolled participants with at least 1 of the PD/Biomarkers evaluated at pre and/or post dose.

8. Immunogenicity analysis set.

The immunogenicity analysis set includes all enrolled participants who receive at least one dose of study treatment and have at least one sample tested for ADA.

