2. INTRODUCTION

Note: In this document any text taken directly from the protocol is *italicized*.

PF-07209960 is a fusion of a single, potency-reduced, IL-15 mutein and a bivalent high affinity anti- PD-1 full length IgG. This antibody-cytokine fusion molecule is designed to deliver PD-1-mediated avidity-driven IL-2/15 receptor stimulation preferentially to PD-1-positive CD8+ T cells, which are enriched in tumors and can mediate anti-tumor activity, while reducing the natural preference of IL-15 for majority PD-1-negative NK cells, which may mediate toxicity. The exposure of the IL-15 mutein is extended by fusing it to an antibody, which also reduces its potency to prevent systemic activation of PD-1 negative lymphocytes. Pre-clinical data suggest the stimulatory activity of PD-1 targeted IL-15 mutein is enhanced in tumor infiltrating lymphocytes preferentially over peripheral lymphocytes and can lead to anti-tumor activity greater than can be achieved with anti-PD-1 and IL-15 agonist either alone or in combination.

Study C4011001 is a FIH Phase 1 study designed to evaluate the safety, tolerability, PK, PD, and potential clinical benefits of PF-07209960 in participants with selected locally advanced or metastatic solid tumors. Presently, only monotherapy of PF-07209960 is assessed in the study, which is composed to two parts; Part 1: Dose Escalation and Part 2: Dose Expansion.

This SAP provides the detailed methodology for summary and statistical analyses of the data collected in study C4011001. This document provides additional details for the planned analyses that are outlined in the protocol. This SAP was written in reference to Amendment 1 of the protocol dated October 30, 2020 which will be the initial version of the protocol that participants will be enrolled under. The original version of the protocol dated September 15, 2020 will not be used. Any major modifications of the endpoints or analyses will be reflected in amendments to the protocol and/or SAP.

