6.2.3. Tumor Response

- Analysis set: Response evaluable set

- Analysis methodology:
 - For treatment response, 'start date' is defined as the first date that a participant received the study intervention.
 - Overall Response Rate (ORR)
 - ORR as assessed using RECIST version 1.1. ORR is defined as the proportion of participants who achieved CR or PR per RECIST version 1.1 (details are provided in the protocol, Section 8.1.1 and Appendix). Both confirmed ORR and uORR will be determined based on the confirmed and unconfirmed CR and PR, definitions provided below.
 - Disease Control Rate (DCR)
 - A participant with a BOR of CR, PR, non-CR/non-PD or SD is defined as having DC. The DC rate is defined as the percentage of participants with DC in the specified analysis set.
 - Best Overall Response (BOR)
 - **Complete Response (CR):** Two objective assessments of CR a minimum of 4 weeks apart documented before PD.
 - **Partial Response (PR):** Two objective statuses of PR or better (PR followed by PR or PR followed by CR) a minimum of 4 weeks apart documented before PD, but not qualifying as CR. Sequences of PR- Stable- PR are considered PRs as long as the two PR responses are observed at a minimum of 4 weeks apart.
 - **Stable Disease (SD)** (applicable only to participants with measurable disease at baseline): At least one objective status of stable disease or better documented at least 6 weeks after 'start date' and before PD but not qualifying as CR or PR.
 - **Non-CR/non-PD** (applicable only to participants with non-measurable disease at baseline): at least one non-CR/non-PD assessment (or better) documented at least 6 weeks after 'start date' and before first documentation of PD (and not qualifying for CR or PR).
 - **Progressive Disease (PD):** Progression documented within 16 weeks after 'start date' and not qualifying as CR, PR or SD.
 - **Not Evaluable (NE):** All other cases. Note that reasons for NE should be summarized and the following reasons could be used:
 - No adequate baseline assessment (defined below).

- No evidence of disease at baseline.
- No post-baseline assessments due to early death, i.e., death prior to 8 weeks after ‘start date’.
- No post-baseline assessments due to other reasons (adequate post-baseline assessments defined below).
- All post-baseline assessments have overall response NE.
- New anti-cancer therapy started before first post-baseline assessment.

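### The SAP's Response Evaluable set requires measurable disease where the protocol requires only a baseline disease assessment, so any Part 1 participant with non-measurable disease only would leave every planned efficacy analysis on that set

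*SAP*

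**What the plan says.** The two documents define the Response Evaluable set differently. After the shared condition of at least one dose, Protocol 9.3 requires that the participant "had baseline disease assessment and at least one post baseline disease assessment". SAP Table 2 says instead: "The response evaluable population will include all participants who received at least one dose of study treatment and had measurable disease at baseline", again with an assessment after baseline.

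Protocol 9.4.2 assigns this one set to all the response and time-to-event endpoints. SAP 6.2.3 (ORR, DCR, best overall response) and SAP 6.2.4 (DOR, PFS, TTP) name the same set.

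SAP 6.2.3 includes a best-response category, non-CR/non-PD, which it describes as "applicable only to participants with non-measurable disease at baseline". Both Protocol 9.4.2 and SAP 6.2.3 count that category as disease control.

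On eligibility, the synopsis says: "Participants entering the study in the expansion cohort have ≥ 1 measurable lesion per RECIST version 1.1". It sets no such condition for Part 1.

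**The concern.** The SAP set shuts out the participants for whom one of its own response categories was written. Non-measurable disease does not prevent observation of progression, death or disease control. Appendix 11 of the protocol also has a response table for non-target disease only, in which CR is a possible status. These participants can therefore contribute to the Part 1 secondary efficacy endpoints, and the protocol's definition would keep them.

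Part 1 activity has some bearing on later steps. The synopsis lets activity in ovarian cancer and MSS CRC in Part 1 prompt consideration of the optional expansion cohorts, and Protocol 4.3.6 lists efficacy among the grounds for advancing a lower dose. The documents do not say that those decisions use this analysis set, so the direct stake is narrower. The reported Part 1 rates and Kaplan-Meier summaries would have a different denominator depending on which document the programmer follows.

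**Working it through.** No sample size, power or stated probability in the plan rests on this definition, so there is no figure to reproduce. The posterior probabilities in Protocol Table 5 concern Part 2, where a measurable lesion is required at entry.

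**1. Compare the sets.** Protocol set: dosed, baseline assessment, later assessment. SAP set: dosed, measurable disease, later assessment. For participants with an adequate baseline assessment, the only difference is measurability.

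**2. Check the category against the set.** The SAP set requires measurable disease, and non-CR/non-PD requires non-measurable disease. No participant meets both, so the count in that row is 0 in the SAP 6.2.3 analyses whatever the data. Appendix 11 agrees: its table for participants with target lesions yields only CR, PR, Stable, PD or NE. SAP 6.2.3 also restricts SD to participants with measurable disease, a restriction with no purpose if everyone in the set has it. The section reads as written for a mixed population.

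**3. Can such participants enrol in Part 1?** The synopsis ties the measurable lesion to expansion. Protocol 5.1 criterion 3, as it reads in the text available, is incomplete: "Participants entering the study in ≥ 1 measurable lesion". Its scope words are absent, possibly through file conversion, so the synopsis is the only complete statement. Appendix 11 lists ascites, effusions and most bone disease as non-measurable, and ovarian cancer is an eligible tumour.

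**4. Size per participant.** Part 1 enrols about 14-22, in cohorts of about 2-4 (Protocol 9.2.1).
- Share of Part 1: 1/22 = 4.5% to 1/14 = 7.1%.
- Share of a dose cohort: 1/4 = 25% to 1/2 = 50%.

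**5. Illustration for DCR.** The documents give neither the share with non-measurable disease only nor an expected DCR. Assumptions: a share of 10% to 30%, a DCR of about 40% in measurable participants, and everyone otherwise evaluable, with counts rounded to whole participants. The protocol-set column runs from none to all of the non-measurable participants having disease control.

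| Part 1 N | Assumed share | Dropped by SAP set | DCR, SAP set | DCR, protocol set |
|---|---|---|---|---|
| 14 | 10% | 1 | 5/13 = 38.5% | 5/14 = 35.7% to 6/14 = 42.9% |
| 14 | 30% | 4 | 4/10 = 40.0% | 4/14 = 28.6% to 8/14 = 57.1% |
| 22 | 10% | 2 | 8/20 = 40.0% | 8/22 = 36.4% to 10/22 = 45.5% |
| 22 | 20% | 4 | 7/18 = 38.9% | 7/22 = 31.8% to 11/22 = 50.0% |
| 22 | 30% | 7 | 6/15 = 40.0% | 6/22 = 27.3% to 13/22 = 59.1% |

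With the exact (Clopper-Pearson) 95% intervals of SAP 5.2.1, the N = 22, 20% row gives 17.3% to 64.3% on the SAP set. On the protocol set it gives 13.9% to 54.9% at the low end and 28.2% to 71.8% at the high end. At a share of 0% the two columns are identical.

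**The case against.** Several points on the other side stand.

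- **The loss is conditional.** Nothing shows that Part 1 will enrol anyone with non-measurable disease only. Criterion 3 is unclear as it reads, and Appendix 11 introduces its non-target-only table with an if.
- **The SAP may depart from the protocol.** Protocol section 9 allows modification where appropriate and asks for an amendment only for major changes to primary endpoint definitions or analyses. Part 1 efficacy is secondary. The fault is an unexplained change that clashes with the SAP's own categories, not a forbidden one.
- **Precision is low under either set.** Part 1 efficacy is descriptive, and the intervals above overlap heavily.

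Three stronger readings are tempting, and the documents do not support them.

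- A reader might infer that non-CR/non-PD can never appear in any output. The mITT set has no measurability condition and may be used for interim and conference summaries, so the category could arise there.
- A reader might infer that the SAP passes off altered wording as verbatim, because it says that "any text taken directly from the protocol is" italicised and this definition is in italics. In the same table the per-protocol entry is italicised and includes a two-cycle dosing condition that the protocol does not contain. Italics there are not a reliable sign of copied text.
- A reader might infer that the Part 2 primary ORR is distorted. Participants there must have a measurable lesion to enter, so the two definitions select essentially the same people.

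**Conclusion.** The inconsistency is real and should be corrected before programming. The SAP's Response Evaluable set is narrower than the protocol's, without explanation, and it conflicts with the best-response and DCR definitions in SAP 6.2.3. Any Part 1 participant with non-measurable disease only would be lost from ORR, DCR, DOR, PFS and TTP as planned.

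The total effect cannot be stated from the documents. Under the assumed 10% to 30% share, 1 to 4 of 14 or 2 to 7 of 22 participants would be dropped, and DCR could shift in either direction. The conclusion assumes that the synopsis gives the intended scope of the measurable-lesion criterion. If that criterion also applies to Part 1, or if no such participant enrols, no participant is lost and only the unused category remains as a wording fault.

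**What to change.** 1. In SAP Table 2, replace the measurable-disease condition with the protocol's baseline disease assessment, so that one protocol-consistent set serves ORR, DCR, DOR, PFS and TTP.
2. Limit only the waterfall plot to participants with measurable disease, because percentage change in tumor size needs measured lesions.
3. If ORR in measurable disease is also wanted, present it as a declared supplementary analysis. Moving the main ORR to that subset would take it off the single set in Protocol 9.4.2, give ORR and DCR different denominators, leave the set for DOR undefined, and ignore that CR is possible with non-target disease only.
4. Complete the sentence in Protocol 5.1 criterion 3 so that it agrees with the synopsis.

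The cost is a SAP wording change and one protocol sentence. Part 1 denominators may rise slightly. No new data are needed, and Part 2 is essentially unchanged.
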